Clinical Research Protocol

Study Title: Radiogenomics of muscle invasive bladder cancer

Protocol Number:	IIT2020-22-[name]-Radiogenomics
Current Version Number:	1.2
Current Version Date:	12 July 2022
Investigational Product:	N/A
IDE Number:	N/A
NCT Number:	NCT04806334
Development Phase:	Pilot
Funding Organization:	Cedars-Sinai
Principal Investigator:	Name: [name], MBA [contact] [contact] E-mail: [contact]
Clinical Site:	Cedars Sinai Medical Center [name]

TABLE OF CONTENTS

PROTOCOL SUMMARY	3
1.0 BACKGROUND, RATIONALE.....	4
2.0 STUDY OBJECTIVES.....	6
3.0 STUDY POPULATION	6
3.1 SELECTION OF THE STUDY POPULATION.....	6
3.2 INCLUSION CRITERIA.....	7
3.3 SUBJECT SCREENING AND ENROLLMENT.....	8
4.0 STUDY DESIGN AND METHODS.....	8
5.0 CLINICAL ASSESSMENT.....	10
6.0 ADVERSE EVENT REPORTING AND DOCUMENTATION.....	11
7.0 DISCONTINUATION AND REPLACEMENT OF SUBJECTS.....	15
8.0 SCHEDULE OF PROCEDURES.....	16
9.0 DATA COLLECTION AND MANAGEMENT	117
10.0 DATA AND SAFETY MONITORING	118
11.0 STATISTICAL CONSIDERATIONS.....	119
12.0 REFERENCES.....	20

PROTOCOL SUMMARY

Title:	Radiogenomics of muscle invasive bladder cancer
Protocol number:	IIT2020-22-[name]-Radiogenomics
Phase:	Pilot
Study Design:	Single center clinical trial evaluating identifying a distinct radiogenomic signature of muscle invasive bladder cancer (MIBC)
Study Duration:	84 weeks
Objective:	Primary Objective: To show feasibility, which we will define as know-how to create a radiogenomic workflow and to learn about the correlation structure between the radiomic and genomic parameters of interest, which will allow us to design future studies with adequate power.
Number of subjects:	20 subjects
Main Inclusion criteria:	Adults with sessile bladder masses, suspected of harboring MIBC
Study product, dose, route of administration:	N/A
Statistical Analysis:	We will apply a deconvolution algorithm to the genomic data from patients with MIBC in conjunction with magnetic resonance imaging (MRI) data to search for genomic and radiomic parameters that predict tumor stage and outcomes.

1.0 BACKGROUND, RATIONALE

In the US, radical cystectomy is the treatment of choice of muscle invasive bladder cancer (MIBC). MIBC comprises approximately 1/3 of bladder cancer (BCa) and is associated with significant morbidity and mortality. Accurate staging of BCa is essential to identifying the optimal treatment. Current NCCN guidelines recommend contrast-enhanced CT of the abdomen and pelvis to assess the local extent of the cancer, including regional lymph nodal. However, 1/3 of patients are understaged, while 1/3 of patients are overstaged with CT imaging (1). Thus, more accurate non-invasive staging modality is necessary, which could improve medical decision making between various treatments (*e.g.*, radical cystectomy vs. bladder preservation).

Radiomics

Multiparametric magnetic resonance imaging (mpMRI) is emerging as the imaging modality of choice in tumor staging, with a reported sensitivity of 90% in detecting BCa and 76% sensitivity with 89% specificity of detecting metastatic lymph nodes (2). The superior soft tissue contrast and versatile imaging sequences of MRI can facilitate margin definitions critical in cystectomy and bladder preservation strategies. In addition, 4D-MRI techniques have provided high isotropic resolution that was previously unachievable with standard MRI (3-5). With these images, extensive quantitative imaging metrics can be collected. Recently, radiomics, defined as the high-throughput extraction of quantitative imaging metrics, has emerged as a potential diagnostic, capable of assessing the tumor's aggressiveness and extent. Thus, 4D-mpMRI offers an opportunity to reduce staging errors through better anatomical visualization (6, 7) compared to traditional CT imaging (8, 9).

Genomics

Genomics has long been the mechanism of assessing a tumor's clinical characteristics. With the advent of early versions of gene expression profiling and RNA sequencing, there has been a large amount of data available for assessing tumor morphology, molecular structure, and behavior. Furthermore, TCGA has reported clustering of mRNA expression converged into distinct subsets with differential epithelial-mesenchymal transition status (*e.g.*, basal, luminal and neuroendocrine), which have been linked to outcomes and survival (10). While we may have more knowledge and understanding of BCa, a different approach to query its molecular underpinning is warranted in hopes of identifying clinically useful biomarkers to guide medical decision making.

A previous study using single cell RNA sequencing (scRNA-seq) demonstrated transcriptional heterogeneity of BCa (11), suggesting that the traditional bulk RNA sequencing (RNA-seq), similar to what is in TCGA, may have limitations in BCa. In particular, scRNA-seq of BCa revealed an interesting transcriptome, a platinum resistance gene, COX7B, and its surrogate marker, CD63, which was previously not identified (12). Consequently, employing scRNA-seq of MIBC, we have identified unique gene clusters including but not limited to EGFR, NRG1, NRXN1, PTPRC, VWF, COL6A2, CD247, and ITGAX (unpublished data). Thus, we believe scRNA-seq hold a key to not only better analyze tumors for genetic defects, but to identify key cell lines within the tumor microenvironment.

Radiogenomics

Radiogenomics is a relatively new area of research, emerging because of the ability to associate radiologic imaging data to genomics data from tumors to garner a better tumor phenotype and predict clinical outcomes (13). Results from these radiogenomic studies have reported a strong

association between radiologic parameters and genomic features, *e.g.*, DNA mutations, mRNA expression, and copy number variations. Imaging parameters with strong associations to genomic data may serve as reliable markers for tumor diagnosis (*i.e.*, staging), prognosis and treatment response. In addition, integrating radiogenomic data may a) allow the exploration of molecular interconnections that explain various tumor features captured by the radiologic parameters and b) validate the mechanistic pathways supporting such interconnections, and thereby, allowing us to gain a deeper understanding of the cancer and its pathophysiology.

The Cancer Genome Atlas (TCGA) is a large publicly available genomic database of various human tumors. Akin to TCGA is The Cancer Imaging Archive (TCIA), a publicly available radiomic database of various human tumors. There are many tumors within TCGA and TCIA with both genomic and radiomic data. For example, Zhu *et al.* integrated multi-omics molecular data with magnetic resonance imaging (MRI) data from 91 invasive breast cancers and reported miRNA expression was associated with tumor size and tumor enhancement texture on imaging (14). Furthermore, Vargas *et al.* evaluated radiogenomic data from 92 high-grade serous ovarian adenocarcinomas and noted a significant association between mRNA expression, miRNA expression, promoter methylation and DNA copy number data with CT-based characteristics of primary ovarian masses, including size, presence of definable mesenteric implants and infiltration, etc. (15). Lastly, Karlo *et al.* reported the radiogenomic results of 233 clear cell renal cell carcinoma cases, which revealed VHL was associated with ill-defined tumor margins, nodular tumor enhancement and gross appearance of intratumoral vascularity (16).

Interestingly, when conducting a PubMed literature search for radiogenomic and BCa, only one article is noted. In this study, Lin *et al.* report the results of bulk RNA-seq, radiomics features and clinical parameters of 62 BCa patients and found that the radiomics and transcriptomics signatures significantly stratified patients into high- and low-risk groups in terms of the progression-free survival (PFS) (17).

Current trends in bladder cancer

The landscape for BCa treatment options have changed dramatically over the past 5 years with the approval of five checkpoint inhibitors as well as Erdafitinib and Enfortumab. For MIBC, more attention is turning towards bladder preservation (BP). Despite improvements in systemic therapy options and radiation therapy technology (*e.g.*, image guide radiation therapy (IGRT), intensity modulated radiation therapy (IMRT), the optimal outcomes (*i.e.*, maintaining one's bladder, good quality of life and overall survival; a.k.a. 'trifecta') is still elusive. There are several factors which may contribute to the inability to obtain this 'trifecta'; including inadequate staging and inability to predict who would respond favorably to radiation therapy. Thus, a more thoughtful, phased approach to BP strategies need to develop and evolve in order to improve long-term outcomes for the growing need of patients who are ineligible for cisplatin based neoadjuvant chemotherapy and/or are either refusing or ineligible for radical cystectomy.

In particular, 5-year OS for MIBC remains poor at 50% (18). However, a patient's quality of life could be negatively affected by radical cystectomy (19), thus the continued intrigue with BP. Multiple BP options exist, although the approach of maximal transurethral resection of bladder tumor (TURBT) performed along with chemoradiation therapy (CRT) is the most favored (20, 21). BP strategies need to develop and evolve if they are to address issues related to OS. Specifically, improved modalities to stage patients with MIBC are needed to ensure we are identifying the optimal patient for BP. With this said, Cedars-Sinai Cancer (CS Cancer) has identified BP strategies as a major initiative from which to begin to develop a BCa center of excellence.

We aim to build upon the current knowledge by correlating radiomics findings with that of genetic signature in order to identify a radiogenomic profile of MIBC which could be used to

[figure not shown]

Fig. 1 Schematic diagram summarizing the interactions of the project

accurately stage patients (Fig. 1) leading to better medical decision making as it relates to BP techniques. Our central hypothesis is that a radiogenomic profile exists that a) is specifically associated with BCa and b) can be utilized to more effectively and accurately stage BCa. We seek to develop a computational algorithm that predicts, from radiographic imaging data and genetic alterations from RNA-seq data of a tumors, the relative proportions of predefined cancer cell populations, which lends to aggressiveness and BCa extent. To begin to test this hypothesis, we propose to conduct a pilot study of integrating radiomics data with genomics data in patients with localized MIBC and correlating to final pathology at the time of radical cystectomy. By improving our ability to better stage patients with MIBC, this work could facilitate future studies to explore a radiogenomic signature associated with MIBC and improve patient outcomes.

2.0 STUDY OBJECTIVES

To show feasibility, which we will define as know-how to create a radiogenomic workflow and to learn about the correlation structure between the radiomic and genomic parameters of interest, which will allow us to design future studies with adequate power.

3.0 STUDY POPULATION

3.1 SELECTION OF THE STUDY POPULATION

The study will accrue patients with sessile appearing bladder masses who are felt by the treating physician to harbor MIBC.

Prior to TURBT at Cedars-Sinai, **ALL** subjects will undergo axial imaging for clinical staging in the form of contrast enhanced MRI of the abdomen and pelvis (standard of care). The pelvic MRI will be multiparametric (mp)-4D MRI incorporating high resolution diffusion weighted imaging (HR-DWI). Both the abdominal and pelvic MRI will have an official interpretation by a radiologist, thus both can be used in the care of the subject. Next, **ALL** subjects will undergo TURBT at which time, voided urine, blood and fresh frozen bladder tumor will be collected.

Many subjects present to Cedars-Sinai after their transurethral resection of bladder tumor (TURBT) at an outside facility and a repeat TURBT is not planned at Cedars-Sinai. Such subjects will undergo axial imaging for clinical staging in the form of contrast enhanced MRI of the abdomen and pelvis (standard of care). The pelvic MRI will be multiparametric (mp)-4D MRI incorporating high resolution diffusion weighted imaging (HR-DWI). Both the abdominal and pelvic MRI will have an official interpretation by a radiologist, thus both can be used in the care of the subject. Next, **ALL** subjects will have their outside TURBT formalin fixed paraffin embedded (FFPE) requested, specifically 1 H&E slide and 10 unstained slides.

Subsequently, those patients deemed to have muscle invasive, yet localized disease and are considered candidates for radical cystectomy by their treating physicians will proceed to radical cystectomy at which time another voided urine, blood and fresh frozen bladder tumor will be collected. Pathologic stage will be determined and reported on both the TURBT specimen and radical cystectomy specimen. Finally, subjects will be followed for 2 years to elicit outcome data.

Inevitably, a portion of subjects with bladder masses who are suspected of harboring BCa will not have bladder cancer (10%), BCa diagnosed may not be MIBC (20%) and some subjects may not desire radical cystectomy for their MIBC (20%), thus we anticipate the need to enroll and image 20 subjects to get to our final study population of 10 MIBC who have undergone mp-4D MRI, TURBT and subsequent radical cystectomy.

3.2 INCLUSION CRITERIA

1. Patients must be > 18 years of age.
2. Patient must have a sessile mass noted within the bladder on cystoscopy or imaging worrisome for bladder cancer, specifically MIBC.
3. Patient must agree to undergo staging which will include mp-4D MRI HR-DWI of the pelvis in addition to standard axial imaging of the abdomen.
4. Patient must have undergone TURBT or agree to undergo planned TURBT as part of the normal treatment course.
5. Patients must not have known or suspected primary urothelial carcinoma of the ureter, urethra, or renal pelvis.
6. Patients must not have known distant metastatic disease (*e.g.* pulmonary or hepatic

metastases). Subjects with malignant lymphadenopathy in the abdomen or pelvis considered appropriate for radical cystectomy and lymphadenectomy with the goal of complete resection of all malignant disease are allowed.

7. Patients must not have had prior definitive treatment for bladder cancer.
8. Patients must not have clinically significant active infection or uncontrolled medical condition that would preclude participation in study.
9. Patients must not have any active malignancy other than urothelial carcinoma of the bladder that, in the opinion of the treating investigator, which could interfere with protocol treatment.
10. Patient must have adequate renal function: Serum creatinine < 2 mg/dL OR calculated CrCl > 30ml/min.
11. Patients must not have allergy or contraindication for MRI contrast/contrast dye.
12. Patients must not be under treatment with systemic immunosuppressive medications (including but not limited to prednisone, cyclophosphamide, azathioprine, methotrexate, thalidomide, and anti-tumor necrosis factor [anti-TNF] agents) within 2 weeks prior to TURBT.
13. Patient must not be adverse to undergo radical cystectomy as part of the normal treatment course if found to have MIBC.
14. Patients must have the ability to understand and willingness to sign a written informed consent.

3.3 EXCLUSION CRITERIA

1. Persons with allergy to animal dander or animal-instigated asthma.
2. Patient must not have undergone a bladder biopsy or limited (incomplete) TURBT within 3 weeks (21 days) of the MRI.

3.4 SUBJECT SCREENING AND ENROLLMENT

Subjects will be recruited by investigators within the outpatient Urology Clinics at Cedars-Sinai Medical Center (CSMC). Subjects will be evaluated by a clinical investigator for eligibility. The study rationale, and potential risks and benefits will be clearly explained; study investigators will obtain informed consents and enroll subjects. Only subjects who meet the inclusion/exclusion criteria will be enrolled. Enrolled subjects will be assigned a unique, non-identifying study subject ID number.

4.0 STUDY DESIGN AND METHODS

This is a single center non-randomized pilot clinical trial assessing radiogenomics in a cohort of subjects with MIBC recruited at CSMC.

After signing informed consent, the subject will be scheduled for standard of care axial imaging of the abdomen and pelvis to include pelvic MRI imaging in the radiologic suite in Davis Building at CSMC.

mp-4D pelvic MRI incorporating high resolution diffusion weighted imaging (HR-DWI)

1. All imaging will be performed on a 3T clinical MR scanner (Biograph mMR, Siemens Medical Solutions, Erlangen, Germany) with a 32-channel phase array surface coil.
2. During the imaging session, routine protocols including 3D T1W volumetric interpolated breath-hold examination (T1-VIBE) with Dixon fat saturation in axial orientation, multi-slice T2W half-Fourier acquisition single-shot turbo spin-echo sequence (T2-HASTE) in axial and coronal orientations, and multi-slice single-shot echo-planar imaging (SS-EPI) DWI sequence will be first acquired for pancreas delineation and tumor definition.
3. 2D Modified Look-Locker Inversion Recovery (MOLLI) sequence in oblique planes to cover as much PDAC tumor mass will be obtained as the reference for in-vivo T1 mapping.
4. Following these sequences, the Multitasking DCE 4D-MRI will be performed. The technique has been designed to cover the entire pelvis. Each SR period lasted 500 ms with 84 TIs at TR 5.6 ms. One readout line will be collected per TI. The SR period will be repeated 1200 times in a scan of 10 min. The DCE temporal footprint was selected to be 1 second by combining two SR periods to balance between the temporal resolution and noise (22).
5. Gd contrast agent (Gadavist, 0.1 mmol/kg, Bayer Schering Pharma) will be administrated intravenously 2 minutes into the scan at a rate of 2 mL/s, followed by a 20 mL saline flush at the same rate. Immediately at the end of this sequence, post-contrast MOLLI at the same slice location as pre-contrast one will be collected. Detailed imaging parameters for the protocols are summarized in “Variables collected”.
6. At the same time the pelvic MRI is being completed, the abdominal MRI can be performed.

Next, subjects who have not had an outside TURBT will undergo TURBT in the operating room (mandatory). In pre-operative holding, a voided urine sample (50 mL) will be collected, while blood (15 mL in ACD-containing tube) and fresh frozen tumor tissue will be collected in the operating room by the BioBank staff. The results of the evaluation of the TURBT will determine if the subject has bladder cancer and if so the histology, clinical stage and grade will be noted. If the subject is found not to have MIBC, then he/she would be off study. For the subjects who had an outside TURBT, tumor material from the TURBT will be requested from the local hospital/pathology, specifically, 1 H&E slide and 10 unstained slides will be requested.

However if the subject is found to have MIBC and is deemed to be a candidate for definitive therapy by radical cystectomy without neoadjuvant chemotherapy or immunotherapy, then he/she will be scheduled for radical cystectomy within 4 weeks. At the time of radical cystectomy, additional voided urine (approximately 50 mL) will be collected in pre-operative holding and blood (15 mL in ACD-containing tube) and fresh frozen tumor tissue will be

collected in the operating room by the Biobank staff. The results of the histological evaluation of the cystectomy specimen will be reported noting histological type of bladder cancer, pathologic stage and grade.

Correlative studies

Embedded within will be crucial correlative studies that will begin to shed light on MIBC in hopes of identifying a radio-molecular staging system, which is more accurate than the standard clinical staging.

These studies will involve analyses of:

(1) Peripheral blood specimen:

An additional specimen of blood will be obtained beyond what is needed for clinical care. The amount of blood will be approximately 15 ml of extra blood collected from a vein into ACD-containing tubes. In the BioBank, the blood will be separated by centrifugation into the plasma fraction and the blood cell fractions. The fractions will be divided into aliquots for measurements which will be done either at the time of the blood sample acquisition or at a designated time later on stored specimens. Storage will be at -80^0 C in a secure biorepository freezer in CSMC BioBank.

(2) Biofluid Specimens (Urine):

Urine sample(s) will be obtained by asking the patient to provide urine into a provided container or via urinary catheter placed at the time of surgery. Approximately 50 mL will be obtained, centrifuged, separated into cellular pellet and supernatant and stored at -80^0 C, in a secure biorepository freezer in CSMC BioBank.

(3) Tissue Specimens:

A fresh frozen tissue sample from TURBT and subsequent cystectomy specimens will be obtained by CSMC BioBank personnel. The tissue samples will be snap-frozen in liquid nitrogen and stored in -80^0 C freezers in CSMC BioBank. When needed for analysis, BioBank will send a portion of the de-identified TURBT tumor (5mm^3) to CS Genomic Core for RNA extraction, and RNA-seq.

Or FFPE tissue sample from a TURBT will be requested. Specifically we will request 1 H&E from the FFPE block with tumor as well as 10 unstained slides.

Using standard techniques, CS Genomic Core will perform RNA-seq. Biostatisticians and Bio-informaticians will assess correlations between radiomics, genomics and pathology data.

Table 8 Correlative Studies timing and requirements

Specimen	Quantity	MRI	TURBT	Cystectomy
Whole Blood ACD tube	1x15 mL+		X+	X+
Urine	50 mL		X+	X+

Bladder tissue (Fresh)	~5mm ³		X~	X+
Bladder tissue (FFPE)	1 H&E 10 unstained		X~	

~, used for sequencing

+, banked in Cedars' Biobank for future use

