9.2 VARIABLES COLLECTED

The following data points/variables will be collected:

1. RNA-seq of bladder tumor
2. Imaging Measurement Tools:
 - MRI Pelvis protocol with modified sequences
 - T1 and T2 imaging (relaxation differences between tumor/tissue)
 - 3D imaging of abdomen (w/o contrast)
 - DWI multi-b value (cellularity, density)
 - 3D imaging of abdomen (w/o contrast)
 - ADC maps for slow and fast diffusion components
 - DCE-MRI (microvascular density, vascularity, vascular permeability)
 - 3D imaging of abdomen (w/ contrast)
 - Kinetic parameter maps, K^{trans} , k_{ep} , v_e , AUC
 - Fractional blood volume, v_p

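### Section 4.0, MRI steps 2 and 3: the pancreas and a pancreatic tumor are named as targets, so the T1 reference and the routine sequences are not prescribed at the bladder lesion

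*Combined protocol and SAP*

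**What the plan says.** The numbered steps in section 4.0 stand under the heading "mp-4D pelvic MRI incorporating high resolution diffusion weighted imaging (HR-DWI". The content that matters here is:

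- Step 2: the routine T1-VIBE, T2-HASTE and diffusion sequences "will be first acquired for pancreas delineation and tumor definition". The diffusion sequence is described as "multi-slice single-shot echo-planar imaging (SS-EPI) DWI sequence".
- Step 3: "2D Modified Look-Locker Inversion Recovery (MOLLI) sequence in oblique planes to cover as much PDAC tumor mass will be obtained as the reference" for T1 mapping.
- Step 4, on the DCE acquisition: "The technique has been designed to cover the entire pelvis".
- Step 5: after the DCE scan, "post-contrast MOLLI at the same slice location as pre-contrast one will be collected". This step also sends the reader to the list of collected variables for the detailed imaging parameters.
- Step 6: the abdominal MRI may be done in the same session, as a scan distinct from the pelvic one.

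Elsewhere the target is the pelvis. Inclusion criterion 3 in 3.2 reads "Patient must agree to undergo staging which will include mp-4D MRI HR-DWI of the pelvis in addition to standard axial imaging of the abdomen". Section 3.1 and the footnote to the schedule in 8.0 also call for a pelvic MRI with high-resolution diffusion imaging. Section 9.2 heads its imaging list as a pelvic protocol, but includes an abdominal 3D entry three times, twice without contrast and once as "3D imaging of abdomen (w/ contrast".

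**The concern.** Steps 2, 3 and 5 are the operative scan instructions, not background text. Eligibility in 3.2 rests on a sessile bladder mass, yet none of the numbered steps names the bladder or a bladder tumor, and two of them name something else. The protocol does not expand the abbreviation PDAC, but with the pancreas named in step 2 the natural reading is pancreatic ductal adenocarcinoma.

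The imaging measurements are one side of every radiomic-genomic correlation the pilot is meant to learn about (2.0), and 11.2 makes high-quality data an explicit aim. Section 11.1 plans 30 radiomic parameters in 10 tumors. Staff who follow the text put the T1 reference in the wrong place. Staff who correct it on the day may place MOLLI slices or choose the diffusion sequence differently from one patient to the next, and with 10 tumors the analysis could not separate that variation from biology. A workflow is also one of the study's deliverables, so its written form matters beyond these patients.

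**Working it through.** The main check sets the passages side by side. The only arithmetic available is the timing of step 4.

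**Timing of the DCE step (inputs from 4.0, step 4).**
- Scan time = saturation-recovery period × repetitions = 0.5 s × 1200 = 600 s = 10 min. The plan states 10 min, so the figure reproduces.
- Readout train = 84 × 5.6 ms = 470.4 ms, which fits within the 500 ms period.
- Temporal footprint = 2 × 0.5 s = 1 s, as stated.

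Step 4 is therefore internally consistent, and it is stated to cover the pelvis.

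**Target of each acquisition as written.**
- Routine T1, T2 and diffusion sequences (step 2): pancreas. No field of view is given, only a purpose.
- Pre-contrast MOLLI (step 3): PDAC mass.
- Post-contrast MOLLI (step 5): tied to the slice location of step 3, so it inherits that target.
- DCE (step 4): whole pelvis, hence the bladder.

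The DCE is the only acquisition in the numbered steps with a stated target or coverage that includes the bladder.

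**What the variables in 9.2 need.**
- Relaxation differences between tumor and tissue on T1 and T2: the T1 reference is the MOLLI, which is not prescribed at the bladder tumor.
- Multi-b diffusion, with ADC maps for slow and fast components: the numbered steps contain only the routine single-shot diffusion sequence. They give no b-values and no high-resolution diffusion step.
- K^trans, k_ep, v_e, AUC and v_p: these come from the DCE data, which cover the pelvis. Nothing in the document makes them depend on MOLLI.

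**Cross-reference.** Step 5 points to 9.2 for detailed imaging parameters. Section 9.2 lists outputs; it gives no b-values, resolution or slice settings.

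**Abdomen entries.** Criterion 3 in 3.2 and step 6 in 4.0 treat abdominal imaging as separate from the pelvic MRI. Three abdominal entries under a pelvic heading therefore need an explanation, and the text does not say whether they are a companion acquisition or mislabelled.

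**Sample size.** The figures in 11.2 (10 analyzed, 20 enrolled, detectable correlation 0.76) use no input from the imaging steps, so none of them moves.

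**The case against.** The strongest reply is that this is leftover wording that nobody would follow. The section is headed pelvic MRI, patients have a bladder mass, and criterion 9 in 3.2 excludes other active malignancy that could interfere, so there would ordinarily be no pancreatic tumor to put slices on. One center and one named scanner are used. Much of this stands: the staff probably will image the bladder. It does not rescue the text, because the prescription then gives no instruction on where the MOLLI slices go and leaves that to each session.

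A reader might infer several stronger things that the documents do not support:

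- *That the protocol as a whole images the pancreas and abdomen instead of the bladder.* The heading, step 4, 3.1, 3.2, 8.0 and the heading of the list in 9.2 all say pelvis, and 9.2 never mentions the pancreas.
- *That the kinetic parameters cannot be derived.* The DCE covers the pelvis with consistent timing, and MOLLI is described only as a reference for T1 mapping. The DCE step itself samples 84 inversion times per period, and the title of the paper cited for it (reference 22) describes fast T1 mapping with the same technique. A misplaced MOLLI loses a comparator, not the maps.
- *That the diffusion maps would miss the bladder.* Step 2 states a purpose, not a field of view. The fault is under-specification.
- *That HR-DWI is omitted from the plan.* It is required in several places. What is missing is its numbered step and its settings, and that gap alone would be a matter of detail.
- *That abdomen in 9.2 should simply become pelvis.* An abdominal MRI is planned, and the indentation of the list may have been lost in the extracted text, so outright replacement could delete an intended entry.

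**Conclusion.** The point holds on the targets in steps 2 and 3. They name the wrong organ and tumor for this trial, and step 5 carries the MOLLI location forward. As written, the T1 reference is not prescribed at the bladder lesion and the routine T1, T2 and diffusion sequences are not directed at it. The unassigned HR-DWI step, the empty cross-reference to 9.2 and the abdomen entries are secondary inconsistencies that belong in the same correction.

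All 20 planned scans fall under the wording, and so do the 10 patients expected to be analyzed. The effect on the correlations cannot be sized: the document does not say which of the 30 radiomic parameters come from which sequence, and how far staff would depart from the text is unknown. The conclusion assumes that PDAC means a pancreatic tumor and that no separate imaging manual, unmentioned in the document, overrides these steps. It should be corrected, but it does not undermine the design or the kinetic part of the imaging data.

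**What to change.** Amend the wording as follows.

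1. In 4.0, steps 2 and 3, replace the pancreas and PDAC wording with the bladder and the index bladder tumor, and state that the pre- and post-contrast MOLLI slices pass through that tumor.
2. State which numbered step acquires the already mandated HR-DWI that feeds the multi-b and slow/fast ADC variables.
3. Either put the imaging settings in 9.2, as step 5 promises, or point step 5 to where they are held.
4. Reconcile the three abdominal entries in 9.2 with the pelvic heading and with the separate abdominal MRI. Say for each whether it belongs to the pelvic protocol, is a companion abdominal acquisition or is an error; do not replace them all by default.

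The cost is a protocol wording amendment. No scan is added beyond those already required, and no sample-size or power figure changes. If patients have already been scanned, recording the MOLLI slice location and the diffusion sequence actually used for each would show whether the data are comparable.
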